Patients will be recruited from the outpatient clinics of the University of Oklahoma Health Sciences Center. Subjects will also be recruited through use of advertisement flyers distributed by campus email and posted in OUHSC clinics. Patients who view the study on ClinicalTrials.gov and have interest in study participation can approach us. They will contact the study coordinator using the telephone number that has been provided on the website. In addition, patients from the Oklahoma Heart Hospital, who meet all study inclusion criteria, will be referred to us by [name], Cardiologist. After informed consent, patients will be randomly assigned (1:1) to active or sham LLTS, stratified by gender. The randomization sequence will be created using randomly chosen block sizes of 4 or 6 and will be implemented through the online REDCap data system. The Parasym device (Parasym Inc) will be used for LLTS or sham stimulation. The device will be connected to a clip electrode that will be attached to the external ear. In the active group, the ear clip electrode will be attached to tragus in the active stimulation group (Figure 4). This device was deemed as non-significant risk by the FDA in our ongoing study (NCT02548274). Moreover, in our ongoing study using this device in

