Blood samples (10cc) will be collected from patients at baseline and 3 months for inflammatory cytokine measurement. At the baseline and 3 months subjects will be asked to complete the Minnesota Living With Heart Failure Questionnaire. At the 1 month visit, the patients will be interviewed by the unblinded physician or clinical coordinator to address any issues with TENS administration at home, and to assess their adherence to the stimulation protocol. A schematic representation of the study design is shown in Figure 5.

Data collection and analysis

Data will be collected by study personnel. Patients will be blinded to the treatment allocation, and every effort will be made to conceal from the study personnel the nature of the intervention in each study arm. The patients will be requested to refrain from discussing the details of their treatment with other patients in the clinic and with the physicians, nurses and the rest of clinic staff. The clinical coordinator and a clinic physician who will not participate in any of the other study related assessments will be unblinded to the treatment allocation and will instruct the patients

on the proper use of the device. These study personnel will be designated to address the patients' questions and concerns as well as to record any side effects related to the use of the device. The final data will be pooled and analyzed by the investigators.

Definition of outcomes

The coprimary outcomes at 3 months are 1) the ratio of the early mitral inflow Doppler velocity to the early diastolic mitral annulus velocity (E/e') and 2) global longitudinal strain (GLS). Secondary outcomes include other echocardiographic parameters [early diastolic mitral annulus velocity (e'), left atrial volume index, tricuspid regurgitation Doppler velocity, ratio of early to late mitral inflow Doppler velocity (E/A), global circumferential strain], 6-minute walk distance, quality of life (assessed by the Minnesota Living with Heart Failure Questionnaire). To ensure rigor, analysis and interpretation of the echocardiographic data, the 6-minute walk test data and inflammatory cytokine data will be performed in a blinded fashion.

Duration of participation:

Enrolled patients will participate in the study for 3 months.

Patient enrollment:

A maximum of 72 patients meeting the inclusion criteria and not meeting the exclusion criteria will be enrolled in the study. The enrollment period is expected to last for at least 18 months.

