Data collection and analysis:

The final data will be pooled and analyzed by the investigators.

E. Statistical methods

Markers of inflammation, 6-minute walk distance and echocardiographic parameters will be compared between groups using repeated measures ANOVA, with 2 time points (baseline, 3 months) and 3 terms included in the model (group effect, time effect, group by time interaction). Significant interactions will be followed by time trend analyses stratified by intervention group. Transformations will be used as appropriate to satisfy modeling assumptions. Analyses will be based on the intention-to-treat principle. A separate per-protocol analysis, analyzing data from all patients who adhered to the TENS protocol at least 80% of the time, will also be performed. Sex will be investigated as a biologic variable by including sex, and interactions with sex, in the ANOVA model. Modification by sex will be explored and interpreted cautiously given that the pilot study is not powered to detect modification by sex. Gene expression array data will be analyzed using a Mann-Whitney U test, adjusting for multiple comparisons using the Benjamini-Hochberg method. Statistical significance will be set at $p<0.025$ for the 2 coprimary outcomes and at $p<0.05$ for all other data.

No formal interim efficacy analyses will be performed. Data quality and protocol implementation, as well as adverse events, will be summarized every six months for the DSMB.

Sample size and power calculations:

For purposes of sample size calculations we have simplified the analysis to focus on the difference in the E/e' ratio between the 2 intervention groups. Assuming a mean \pm standard deviation E/e'

ratio 11.1 ± 4.4 ²⁸ and 30% reduction in the LLTS group¹⁹, 72 patients would provide 80% power to detect the specified effect sizes at a two-sided α level of 0.025. The same sample size, under similar assumptions and a baseline GLS 16.1 ± 2.2 , would provide 90% power to detect an absolute 1.8% difference in GLS between the 2 groups.

F. Gender/Minority/Pediatric Inclusion for Research

Participants will be age 18 or older. Race, minority status and gender will not affect enrollment.

G. Human participants

72 participants of any gender/ethnic group, age 18 to 90 will be included.

Inclusion Criteria:

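### Randomisation is stratified by sex, but the coprimary model has no sex or sex-by-time term, so the test is slightly conservative if 3-month change differs by sex

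*Combined protocol and SAP*

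**What the plan says.** In section D (Research design and Methods, Aim 1), "patients will be randomly assigned (1:1) to active or sham LLTS, stratified by gender", with "randomly chosen block sizes of 4 or 6".

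Under Definition of outcomes, the coprimary outcomes are E/e' and GLS, both at 3 months. Section E (Statistical methods) analyses the echocardiographic parameters, which include both, by "repeated measures ANOVA, with 2 time points (baseline, 3 months" and "3 terms included in the model (group effect, time effect, group by time interaction". Sex is not among those terms. Each coprimary is tested at 0.025.

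Later in the same paragraph: "Sex will be investigated as a biologic variable by including sex, and interactions with sex, in the ANOVA model". The next sentence limits that work: "Modification by sex will be explored and interpreted cautiously given that the pilot study is not powered to detect modification by sex". The section does not say whether the sex terms belong to a second model, nor which model gives the coprimary p-values.

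**The concern.** A factor used to stratify the randomisation is normally carried into the primary analysis. If it is left out although it predicts the response, the arms are balanced on it but the standard error does not reflect that balance. The standard error is then too large, and the test rejects less often than its nominal level.

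Here the relevant term is specific. With two time points the group-by-time test equals a two-sample test on change from baseline, so a sex main effect, being constant over time, cancels. Only a sex difference in change (sex-by-time) remains in the error. Adding sex alone would do nothing for this test.

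The second matter is wording. The sex sentence refers back to the ANOVA model without calling the sex analysis separate. An analyst could fit one model with every term in it and read the coprimary p-value from its group-by-time row.

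**Working it through.** **Inputs from the documents.** 72 patients, 36 per arm; two-sided alpha 0.025 per coprimary; E/e' mean 11.1, SD 4.4, 30% reduction; GLS SD 2.2, difference 1.8 (Sample size and power calculations). The pilot had 60% women (section C).

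**Assumptions.** 60% women in this trial, taken as 22 women and 14 men per arm; SD of change equal to the stated SD; sex explains a share R² of the variance in change, with R² = 0, 2%, 5% or 10%. The SD of change equals 4.4 when the within-patient correlation is 0.5, because 4.4 × √(2 × (1 − 0.5)) = 4.4. The documents give neither the correlation nor R².

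**1. The plan's own figures.** E/e': 0.30 × 11.1 = 3.33, and d = 3.33/4.4 = 0.757. GLS: d = 1.8/2.2 = 0.818. The standard error in SD units is √(2/36) = 0.2357. Noncentral-t power with 70 df is 81.9% for E/e' (83.4% by normal approximation; plan 80%) and 87.8% for GLS (89.1% by normal approximation; plan 90%). The plan's figures reproduce within about 2 points.

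**2. A sex main effect alone.** Simulation of 8,000 null trials with blocks of 4 or 6 within sex, a constant sex difference of 2 units and no sex-by-time effect: mean standard error 1.033 with or without sex in the model, and type I error 0.027 either way (nominal 0.025, simulation error about 0.002). Omitting a pure main effect costs nothing.

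**3. A sex difference in change.** Total variance is held at 1. The three-term test was simulated with sex exactly balanced between arms. For the model with sex and sex-by-time, the standard error is √((2/36) × (1 − R²)) with 69 df. At R² = 5%, for example, it is √(0.05556 × 0.95) = 0.2297.

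| R² | Three-term type I error | E/e' power, three-term → adjusted | GLS power, three-term → adjusted |
|---|---|---|---|
| 0 | 2.5% | 81.90% → 81.88% | 87.84% → 87.82% |
| 2% | 2.4% | 82.1% → 82.7% | 88.2% → 88.5% |
| 5% | 2.2% | 82.5% → 84.0% | 88.4% → 89.5% |
| 10% | 1.8% | 83.0% → 86.0% | 89.0% → 91.1% |

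Three-term power also rises down the table because total variance is fixed, so the within-sex variance shrinks as R² grows.

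The R² values convert to a sex difference in change of √(R² / ((22/36) × (14/36))) SDs: 0.29, 0.46 and 0.65 SD.

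**4. Cross-check with the planned blocks.** Here the within-sex SD of change is fixed at 4.4 and the effect is 3.33 in both sexes. E/e' power, three-term against adjusted, is 81.8% and 82.0% with no sex difference in change, and 79.4% and 81.1% with a difference of 2.2 (half an SD). That difference corresponds to R² = 0.24 × 2.2² / (0.24 × 2.2² + 4.4²) = 5.7%, and the gain agrees with the 5% row. Type I error of the three-term test there is 0.022.

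**5. If all group-by-sex interactions sat in the model giving the p-value.** The result depends on the test used (E/e', R² = 0, 68 df):

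- Sequential sums of squares with sex entered first, or Type II: group-by-time has the same sum of squares as in the sex-adjusted model; power 81.86%.
- Marginal test, equal weight to the sexes: standard error √(0.25 × (2/22 + 2/14)) = 0.2417; power 79.7%.
- Reference coding, one sex only: standard error √(2/22) = 0.3015 for women or √(2/14) = 0.3780 for men; power 59% or 39%.

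With assumed effects of −1.5 in men and −4.55 in women (0.4 × −1.5 + 0.6 × −4.55 = −3.33), the group-by-time row averaged −3.33 in the three-term model, −3.02 under equal weighting and −1.49 with men as reference.

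**The case against.** The strongest reply is that nothing here is broken. Stratified blocks balance the arms by sex whatever model follows. Leaving sex out cannot inflate the false-positive rate. A gain needs a sex difference in change, and the documents give no evidence of one. Three-term power for E/e' stays above the planned 80% in every row of the table, and the gain is at most 3 points. The unstated within-patient correlation matters far more: E/e' power on change is 66%, 82% or 97% at correlations of 0.3, 0.5 or 0.7. All of this stands, and it sets the size of the point. It does not remove the case for adjusting by a factor the trial already stratifies on, because that costs almost nothing when the factor is irrelevant.

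A reader might infer two stronger things.

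- **That the stratification is wasted or the test invalid.** The documents do not support this: balance is kept, and the error runs in the conservative direction.
- **That the plan puts treatment-by-sex interactions into the confirmatory test, so that the coprimary p-value answers a different question at 39% or 59% power.** The plan calls modification by sex exploratory and unpowered, so a supplementary model is the more natural reading. The low figures also need single-sex reference coding. Under Type II tests, or sequential tests with sex entered first, the group-by-time comparison is unaffected. If the effect is the same in both sexes, even marginal tests cost only precision.

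What remains of the second inference is a gap in wording. The same paragraph uses the word separate for the per-protocol analysis but not for the sex analysis.

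**Conclusion.** The point holds as a modest, nearly free improvement. The three-term model ignores a factor used in the randomisation, and if 3-month change differs by sex, the group-by-time test is slightly conservative. Over the assumed range of 2% to 10% of variance explained, the true level is 2.4% to 1.8% against a nominal 2.5%. The forgone power is about 0.6 to 3 points for E/e' and 0.3 to 2.1 points for GLS. If sex explains nothing, adjustment loses about 0.02 points. These sizes rest on 36 analysed patients per arm, 60% women, the plan's SDs applied to change, and R² values that the documents do not supply.

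The sex-interaction sentence needs clarification only. It is not evidence that the coprimary test has been misspecified.

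**What to change.** In section E:

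- State one model for the coprimary p-values: group, time, group-by-time, sex and sex-by-time, with no group-by-sex term. If the 3-month value is to be the response, include sex as a covariate instead. Use the sex variable on which randomisation was stratified.
- Add that the model with group-by-sex interactions is fitted separately as the exploratory analysis already described, and that no coprimary p-value is taken from it. The reason is that under marginal tests or reference coding its group-by-time row can be an equal-weight or single-sex effect.

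The cost is two sentences and one residual degree of freedom (70 to 69). Sample size, data collection and the planned look at sex as a biological variable do not change.

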Echocardiography will be performed at baseline and at 3 months to assess diastolic function (Acuson SC2000, Siemens). Two-dimensional long axis and short axis LV images will be obtained and Pulse-wave Doppler spectra of mitral inflow (E and A waves) and mitral annulus tissue Doppler spectra will be recorded. The early diastolic mitral annulus velocity (e') will be used to assess diastolic function as previously described^{24,25}. The ratio of early to late mitral inflow Doppler velocity (E/A ratio) is a marker of LV diastolic relaxation and stiffness, and the E/e' ratio correlates well with LV filling pressures^{24,25}. In addition, LV diastolic strain, a sensitive marker of diastolic LV function, which independently predicts outcomes in patients with HFpEF^{25,26}, will be obtained off-line using a speckle-tracking algorithm (Acuson SC2000 eSie VVI™). Analysis and interpretation of the echocardiographic data will be performed in a blinded fashion. A 6-minute walk test, a well validated measure of exercise capacity in heart failure²⁷, will be performed at baseline and 3 months. A 5-min ECG and a 10 second ECG will be performed at baseline and at 3 months to measure heart rate variability, a marker of vagosympathetic balance. To ensure rigor and avoid bias, participants will be encouraged to return for the 3-month post-treatment assessment regardless of their adherence status.

Aim 2. To examine the effect of intermittent (1 hour daily for 3 months) LLTS on inflammatory cytokines relative to sham stimulation, in patients with HFpEF.

[figure not shown]
The same group assignment described in Aim 1 will be used for Aim 2. Blood samples (10ml) will be collected at baseline and at 3 months for cytokine measurement. Samples will be centrifuged (4000g for 10 min), and serum will be stored in aliquots at -20°C until assayed. Patients' serum will be saved frozen and processed in batches of 10 to 12. Inflammatory cytokines, including TNF- α , IL-1 β , IL-6 and IL-18 will be measured using commercially available multiplex assays. In addition, RNA will be isolated from whole blood using the TempusTM RNA isolation tubes (ThermoFisher Scientific Inc., Waltham, MA), cDNA will be generated and gene expression of inflammatory cytokines and chemokines will be quantified using a Qiagen RT² Profiler PCR Array (PAHS-150Z), relative to the geometric mean of 5 stable reference genes. The investigators

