performing the cytokine assays will be blinded to group assignment to ensure rigor. All assays will be run at the [name] Lab at the University of Oklahoma Health Sciences Center.

In addition, we will perform exploratory analyses in order to determine relationships between clinical and cytokine responses to LLTS and identify predictors of response based on baseline cytokine levels. It is known that vagus nerve stimulation attenuates inflammation through the cholinergic anti-inflammatory pathway^{12,14-17}. If this pathway is important in HFrEF as well, we expect that the decrease in cytokines will be correlated with the effect on echocardiographic markers of diastolic dysfunction and/or improvement in exercise capacity.

We intend to recruit 72 patients. Patients will be enrolled in the study over 15 months and the total duration of the study including follow-up will be 18 months, allowing for 3 months of startup and 3 months close-out. Patients will be followed with 3 outpatient visits (baseline, 1 month and 3 months). During the baseline visit, a complete history and physical examination will be done by one of the investigators. In addition, patients will be instructed on how to use the TENS device and attach the electrode clip on the respective site based on their randomization group, and will be asked to repeat the process themselves under direct supervision, to ensure correct use of the device. This process will be done by a clinical coordinator and/or physician who is unblinded to random allocation.

At each follow-up visit, patients will have a brief history and physical examination, and any cardiovascular events will be recorded. In addition, the discomfort threshold for tragus stimulation

will be obtained to ensure that patients are receiving adequate stimulation. Patients will undergo echocardiography at baseline and 3 months to assess diastolic function. A 6-minute walk test will be performed at baseline and 3 months to assess exercise capacity. A 5-min ECG and 10 second ECG will be performed at baseline and 3 months.

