Clinical staff will track the following from patient report, physical assessments and documentation of clinical emergencies, adverse events according to federally published grading (0=no adverse event; 1=mild; 2=moderate; 3=severe and undesirable adverse events; 4=life threatening/disabling; or 5=death) and attribution (1=unrelated; 2=unlikely; 3=possible; 4=probable; 5=definite) scales. Clinical staff will report findings to the Investigator, who will then advise the IRB, NIH and FDA as indicated. Given the mild risk nature of the study, composite reports will be reviewed every ten patients to assure that untoward events do not occur systematically, and dropout cases will be reviewed singly to learn whether further inquiry or modifications should be made to improve study implementation.

b. Adverse event (AE) grading

0=no AE; 1=mild; 2=moderate; 3=severe and undesirable AE; 4=life threatening/disabling; or 5=death

c. Plan for unanticipated AE reporting:

Unanticipated AE will be reported to the IRB.

d. Plan for annual reporting of AEs:

Use of IRB forms for reporting. Our data sheet will have a column detailing any AEs that might occur.

e. *Interim efficacy analysis is not applicable to this study.*

2. *Data and Safety Monitoring Board (DSMB) that will be responsible for monitoring the study:*

- Institutional studies provide:
a. Chair, members

[name]

[name]

b. Frequency of safety reviews:

After each study

I. Literature sited

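### The co-primary test is a change-score comparison that patients without a 3-month echo do not inform, and the plan states no missing-outcome assumption or sensitivity analysis behind its intention-to-treat label

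*Combined protocol and SAP*

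**What the plan says.** Section E (Statistical methods) compares the echocardiographic parameters between groups by "repeated measures ANOVA, with 2 time points (baseline, 3 months) and 3 terms included in the model": group, time and their interaction. It then states "Analyses will be based on the intention-to-treat principle" and adds a second analysis set: "A separate per-protocol analysis, analyzing data from all patients who adhered to the TENS protocol at least 80% of the time".

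Section D (Definition of outcomes) names E/e' and GLS at 3 months as co-primary. Each is measured twice only: "Patients will undergo echocardiography at baseline and 3 months to assess diastolic function". The 1-month visit has no echo.

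On retention, Section D (Aim 1) says "participants will be encouraged to return for the 3-month post-treatment assessment regardless of their adherence status". Section H foresees losses: "dropout cases will be reviewed singly to learn whether further inquiry or modifications should be made". Section D (Patient enrollment) makes 72 the maximum enrolled, and Section E makes 72 the number that gives the stated power.

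The plan does not define the intention-to-treat set. It names no estimation method that retains incomplete patients, no imputation, no missingness assumption and no missing-data sensitivity analysis. Section E does cover the model, transformations, the per-protocol set, sex, multiplicity and power, so this looks like an omission and not removed text.

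**The concern.** Intention-to-treat tells a reader that every randomised patient counts in the comparison as assigned. The named method does not deliver that for a patient whose 3-month echo is missing: such a patient has no change score and adds nothing to the group-by-time test.

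Two things are at stake. First, the change-score comparison among patients with both echoes is biased if dropout depends on baseline severity differently in the two arms, whereas a comparison that conditions on baseline is not. Second, if dropout depends on the 3-month value that was never seen, neither approach is safe, and the plan offers no way to show how far the conclusion depends on those patients.

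**Working it through.** **Inputs.** From Section E: E/e' mean 11.1, SD 4.4, 30% reduction; GLS SD 2.2, difference 1.8; two-sided alpha 0.025; N = 72. From Section D: 1:1 allocation, so 36 per arm. Assumed, because the documents give neither: the missing rate, and a baseline-to-3-month correlation ρ of 0.5 unless stated.

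**1. The plan's own figure.** The E/e' effect is 0.30 × 11.1 = 3.33. The standard error is 4.4 × √(2/36) = 1.04, and 3.33/1.04 = 3.21. The normal approximation gives power Φ(3.21 − 2.24) = 83%; the noncentral t gives 81.9%. The stated 80% is reproduced. For GLS the results are 89.1% (normal) and 87.8% (t), against a stated 90%. The sample size is not at fault on this point.

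**2. What the test is.** With two time points, the group-by-time contrast is (mean change, LLTS) − (mean change, sham). Change = Y3 − Y0 needs both echoes.

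**3. Power if only complete pairs count** (noncentral t, missing rates assumed):

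| Missing | Per arm | E/e' | GLS |
|---|---|---|---|
| 0% | 36 | 81.9% | 87.8% |
| 5% | 34 | 79.4% | 85.7% |
| 10% | 32 | 76.6% | 83.3% |
| 20% | 28 | 70.0% | 77.3% |

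**4. Bias when dropout depends on baseline.** Assume no treatment effect and let z be standardised baseline E/e'. Let the probability of a missing echo be logistic(−2 + z) on LLTS and logistic(−2 − z) on sham. Each arm then loses 15.5%, and mean z among those observed is −0.137 on LLTS and +0.137 on sham. Since E(change | z) = −(1 − ρ) × 4.4 × z, the change-score difference is (1 − 0.5) × 4.4 × (0.137 + 0.137) = +0.60. Simulation gave +0.61. A model that conditions on baseline gave about 0. Swapping the arms gives −0.60. The size is 0.60/3.33 = 18% of the planned effect.

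**5. Bias when dropout depends on the unseen value.** Again assume no effect. Missingness on LLTS now follows logistic(−2 + z3), with z3 the standardised 3-month value; sham is unrelated to outcome (about 14% missing overall). The change-score difference is −0.30 and the baseline-conditioned one −0.46; negative appears to favour LLTS. Here conditioning on baseline does worse.

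**6. Precision.** Per-patient variance, in units of the outcome variance, is 2(1 − ρ) for change and 1 − ρ² for a baseline-conditioned comparison. The ratio is (1 + ρ)/2. At ρ = 0.5 that is 1.00 against 0.75.

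**7. Direction.** Suppose a fraction m of LLTS patients is missing, none of them benefited, and sham losses are neutral. The observed effect is then overstated by 1/(1 − m): 5%, 11% and 25% at m = 0.05, 0.10 and 0.20. On 3.33 this is 0.18, 0.37 and 0.83 units. Now suppose instead that 10% of sham patients are missing and are 3.33 units worse than the sham patients seen, with LLTS losses neutral. The true sham mean is then 0.10 × 3.33 = 0.33 higher than observed, and the effect is understated by 0.33. Both scenarios are possible.

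**The case against.** The plan never says that incomplete patients are dropped. That follows from the classical fit of the named method. A maximum-likelihood fit would keep baseline-only patients, and the plan could be read to allow one. This stands as a limit: the text leaves the handling unstated. It does not remove the gap, because no such fit is named.

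A reader might infer that the co-primary analysis is restricted to patients who kept up the treatment. The documents do not support that. Patients are encouraged to return whatever their adherence, and the 80% rule applies only to the separate per-protocol analysis. Those who stop stimulating but attend at 3 months are analysed as randomised.

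A reader might also infer that losses favour the active arm. That is unsupported too. Section D gives sham patients the same daily hour and the same titration to discomfort, at the ear lobe. If patients leave for lack of benefit and LLTS works, sham could lose more non-improvers, which would work against LLTS.

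It is also fair to say that, with echo at only two times, baseline-only patients add no information on the treatment contrast. A likelihood model with a common baseline mean gives the same contrast as ANCOVA in patients with both echoes. The gain is a weaker missingness assumption and better precision, not recovered outcomes. This is why the sensitivity analysis is needed.

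The adherence above 90% reported in Sections C and D does not settle the matter. It is a preliminary figure for stimulation in paroxysmal atrial fibrillation, not an echo completion rate in this trial.

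**Conclusion.** The point holds in a limited form. The group-by-time test of the co-primaries is a change-score test that, as classically fitted, rests on patients with both echoes. The plan calls the analysis intention-to-treat without defining the set, stating a missingness assumption or testing one. The issue concerns missing 3-month echoes, not non-adherence.

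Neither the rate of missing echoes nor the direction of bias is known from the documents. The 0.6-unit bias rests on an assumed correlation of 0.5, about 15.5% missing, and opposite dropout patterns by arm, which nothing in the documents predicts. The 1/(1 − m) figures are one scenario among several; at m = 0.05 or 0.10 they lie well inside one standard error (1.04). With every echo obtained there would be no missing-data bias, and only the precision argument would remain. The plan should be amended before analysis.

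**What to change.** In Section E, for E/e' and GLS:

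- Define the analysis set as all randomised patients, analysed as assigned.
- Replace the group-by-time ANOVA with a baseline-conditioned comparison at 3 months, adjusted for the sex stratum: either a constrained likelihood model with a common baseline mean, or ANCOVA. State that it assumes outcomes are missing at random given the variables in the model.
- Add a delta-adjusted (tipping-point) sensitivity analysis. Shift the missing 3-month values by δ separately in each arm and report the shifts at which the conclusion changes. The contrast moves by about m_LLTS × δ_LLTS − m_sham × δ_sham, where m is the fraction missing in the arm. The scenario in which missing LLTS patients had no benefit is then one point on the grid.

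The first two changes remove bias from baseline-dependent dropout and improve precision. Only the third addresses dropout that depends on the unseen value. The cost is a short rewrite of Section E and a small amount of programming. Baseline echo and sex are already collected, so no new data are needed.

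### The gene-expression test is valid, but it has no baseline or sex term and does not say which value it compares; a rank-based baseline adjustment would usually recover power

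*Combined protocol and SAP*

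**What the plan says.** - **Test.** Section E (Statistical methods): "Gene expression array data will be analyzed using a Mann-Whitney U test", with Benjamini-Hochberg correction across genes. No covariate, stratified version or analysis variable is named. Outside the two coprimary outcomes, significance is set "at $p<0.05$ for all other data".
- **Samples.** Section D, Aim 2: "Blood samples (10ml) will be collected at baseline and at 3 months for cytokine measurement". The same section says that "gene expression of inflammatory cytokines and chemokines will be quantified" from whole-blood RNA, relative to 5 reference genes. No separate RNA sampling time is given. Baseline and 3 months are the only blood-draw times anywhere in the protocol, so a baseline RNA sample is implied, not stated.
- **Randomisation.** Section D, Aim 1: patients are "randomly assigned (1:1) to active or sham LLTS, stratified by gender".
- **Other markers.** Section E gives inflammation markers, walk distance and echocardiographic parameters a "repeated measures ANOVA, with 2 time points (baseline, 3 months) and 3 terms included in the model". Sex enters that model to explore whether it modifies the effect.
- **Status.** Gene expression belongs to Aim 2. It is not among the coprimary or secondary outcomes listed in Section D, and Section E gives no power figure for it.

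**The concern.** Two samples per patient appear to be available, but the named test uses one number per patient. There are two ways to supply that number, and the plan does not choose between them:

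- The 3-month value leaves baseline unused.
- The change from baseline uses it, but adds baseline noise when the within-patient correlation is low.

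Which is better depends on a correlation that the plan does not give and that will differ between genes. The choice also stays open until data are in hand. At stake is the chance of detecting true transcript changes in Aim 2, where multiplicity correction across an array already tightens the per-gene threshold. No error rate is inflated.

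**Working it through.** **Inputs from the protocol.** 72 patients allocated 1:1, so 72/2 = 36 per arm; stratification by gender; blood at baseline and 3 months; Benjamini-Hochberg across genes.

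**Assumed, because the protocol does not give them.** True shift 0.6 SD; baseline to 3-month correlation ρ from 0 to about 0.85; a per-gene threshold of 0.01 standing in for Benjamini-Hochberg, which has no fixed per-gene threshold; normal data unless stated.

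**The plan's own power figures.** None concerns gene expression. As a check on 36 per arm: for E/e', the difference is 0.30 × 11.1 = 3.33 and 3.33/4.4 = 0.757 SD, which at two-sided 0.025 gives 81.9% (t) against the stated 80%. For GLS, 1.8/2.2 = 0.818 SD gives 89.1% (normal approximation) or 87.8% (t) against the stated 90%. The sample size is taken as given.

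**Why baseline adjustment helps.** Take the variance of the group difference in 3-month values as 1, with equal variance at both times. On the linear scale:

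- change from baseline: 2(1 − ρ)
- baseline-adjusted: 1 − ρ²

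| ρ | 3-month value | Change | Adjusted |
|---|---|---|---|
| 0.3 | 1 | 1.40 | 0.91 |
| 0.5 | 1 | 1.00 | 0.75 |
| 0.7 | 1 | 0.60 | 0.51 |

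Change beats the 3-month value only when 2(1 − ρ) < 1, that is, ρ > 0.5. Because 1 − ρ² = (1 − ρ)(1 + ρ) ≤ 2(1 − ρ), adjustment is never worse than either, apart from the degree of freedom it uses.

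**Simulated power, normal data, threshold 0.01, shift 0.6 SD.** Rank ANCOVA here regresses ranked 3-month values on group and ranked baseline.

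| ρ | Mann-Whitney, 3-month | Mann-Whitney, change | Rank ANCOVA | Gain over 3-month | Gain over change |
|---|---|---|---|---|---|
| 0 | 44% | 19% | 45% | 1 | 26 |
| 0.3 | 44% | 30% | 49% | 5 | 19 |
| 0.5 | 43% | 45% | 58% | 15 | 13 |
| 0.7 | 42% | 70% | 75% | 33 | 5 |

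At ρ of about 0.85 rank ANCOVA no longer gains over the change test. With no true effect, every method rejected in about 1% of trials. Repeat runs differ by 1 to 2 points.

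**A second setting** (threshold 0.05, shift 0.67 SD, rank ANCOVA with baseline and sex), in the order 3-month / change / rank ANCOVA:

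- ρ = 0: 78.5 / 48.3 / 78.1%
- ρ = 0.3: 79.0 / 63.5 / 81.0%
- ρ = 0.5: 77.5 / 77.9 / 86.9%
- ρ = 0.7: 77.2 / 93.7 / 95.5%
- ρ = 0.8: 76.9 / 98.9 / 98.9%

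The pattern is the same with smaller differences.

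**Heavy tails** (t components with 3 degrees of freedom, threshold 0.01):

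| ρ | Mann-Whitney, 3-month | Mann-Whitney, change | Linear ANCOVA | Rank ANCOVA |
|---|---|---|---|---|
| 0.3 | 68% | 50% | 58% | 75% |
| 0.5 | 68% | 68% | 68% | 82% |
| 0.7 | 69% | 91% | 85% | 92% |

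Linear ANCOVA loses 68 − 58 = 10 points to the 3-month test at 0.3 and 91 − 85 = 6 points to the change test at 0.7. Rank ANCOVA does not lose to either.

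**Sex.** With an assumed 0.5 SD sex effect, adding sex to a linear model that already contains baseline gained about 0 to 1.5 points (threshold 0.05, shift 0.67 SD).

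**The case against.** The other side is strong on several points.

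- **A reader might infer that the named test throws baseline away.** The text does not support that: the analysis variable is unstated, and Mann-Whitney on change uses baseline. At a correlation of 0.7 or more it recovers most of the gain. This stands.
- **A reader might infer that transcripts are handled worse than serum cytokines.** With two time points and complete data, the group-by-time term of the repeated measures ANOVA is a t-test on change, and Mann-Whitney on change is its rank analogue. At ρ = 0.3/0.5/0.7 simulated power is 31/48/73% for the t-test and 28/45/70% for the rank test. If change is intended, the two are handled about alike. This stands.
- **A linear ANCOVA is not a free improvement.** The heavy-tail results bear this out, and a rank method is a reasonable guard for expression data. Log scaling may shorten the tails, but the protocol gives no distribution. This is why the adjusted test should itself be rank-based.
- **Leaving out sex costs little power.** Agreed. The case for including it is that it is the stratification factor.
- **The stakes are low.** Gene expression is an unlisted measure in a pilot study, multiplicity is handled, and the test is valid. Agreed.

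What survives is that neither version of Mann-Whitney does well across the range of correlations. Rank ANCOVA matched or beat both to within 1 point in every normal and heavy-tailed scenario tried.

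**Conclusion.** The point holds as an efficiency improvement and a gap in specification, not as an error. The plan names an unadjusted test and leaves its analysis variable open. In the normal-data setting at threshold 0.01, rank adjustment for baseline adds about 5 to 33 points over the 3-month test for correlations of 0.3 to 0.7, and about 19 down to 5 points over the change test. The gain over the 3-month test nearly vanishes at correlation 0, and the gain over the change test vanishes at about 0.85. In the second setting the gains are smaller.

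These sizes rest on assumed values for the effect, correlation, threshold and distribution, and on RNA being drawn at baseline. They do not show that Aim 2 will miss true gene changes; a reader who concluded that would be going beyond what the documents give. The coprimary analyses are unaffected.

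**What to change.** Amend the gene-expression sentence in Section E, and the RNA sentence in Section D, Aim 2, to say:

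1. Whole-blood RNA is sampled at baseline and 3 months. If no baseline RNA is planned, the baseline part of this point falls away.
2. For each gene, the primary test is a rank-based ANCOVA: 3-month expression (delta-Ct relative to the 5 reference genes), ranked across both arms, regressed on group, ranked baseline and sex. Sex is included as the stratification factor.
3. Benjamini-Hochberg across genes is kept.
4. A linear ANCOVA on the log (delta-Ct) scale with the same terms is the supporting estimate, since ranks give no effect size on the expression scale.
5. How patients without a baseline RNA sample are handled.

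The cost is a few sentences and slightly more analysis work. If RNA is drawn at both visits as implied, no new samples, visits or patients are needed. The one new burden is the rule for missing baseline samples.
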